3.5 DETERMINATION OF SAMPLE SIZE

The sample size has been selected without performing a power calculation to provide descriptive information on the safety, tolerability, and PK following administration of RP3128. This trial enrolled up to 56 HV (32 in SAD and 24 in MAD). Number of subjects enrolled in this study is in line with standard phase I studies and is considered sufficient to provide descriptive information on the pharmacokinetics, safety and tolerability of RP3128 while minimizing exposure to humans. The actual number of dose cohorts will depend upon the emerging safety data.

3.6 TREATMENT ASSIGNMENT

Subjects who entered the treatment phase was assigned a unique 4-digit randomization number in the format of XYZZ to identify study part (X), cohort number (Y) and subject identifier (ZZ). The first 2 randomization numbers XY01 and XY02 in each cohort represents the sentinel subjects in Part number X and cohort number Y. For SAD and MAD parts, X is 1 and 2 respectively. For the SAD part, number Y is denoted by 1 to 5 for 5 cohorts, whereas for MAD part the number Y is denoted by 1 to 3 for 3 cohorts. Once any subject or randomization number is assigned, it cannot be reassigned to any other subject.

Allocation to treatment was based on a predetermined random order. Randomization to RP3128 or placebo took place for each cohort separately. The randomization lists were generated by an unblinded staff at Inflammax Research using the computer program Statistical Analysis System (SAS[®]) and managed according to the site's standard operating procedures (SOPs). Separate randomization ratios were used for study SAD Part and MAD Part as indicated in the tables below.

Dose escalation cohorts for Part 1 (SAD)

Cohort	Dose level	n	Sentinel cohort RP3128: Placebo	Remaining cohort RP3128: Placebo	Total cohort RP3128: Placebo
S1	25 mg	4	1:1	2:0*	3:1
S2	50 mg	6	1:1	3:1	4:2
S3	100 mg	6	1:1	3:1	4:2
S4	200 mg	8	1:1	5:1	6:2
S5	400 mg	8	1:1	5:1	6:2

*Single blind (subject)

Dose escalation cohorts for Part 2 (MAD)

Cohort	Dose level	N	Sentinel cohort RP3128: Placebo	Remaining cohort RP3128: Placebo	Total cohort RP3128: Placebo
M1	25 mg	8	1:1	5:1	6:2
M2	100 mg	8	1:1	5:1	6:2
M3	400 mg	8	1:1	5:1	6:2

3.7 ADMINISTRATION OF STUDY MEDICATION

Depending on the cohort, specific dose/doses of RP3128/placebo was dispensed by pharmacy staff during the study. RP3128/placebo capsules was administered orally in the morning with approximately 240 mL (8 fluid ounces) of water at room temperature by the subject. For SAD part, the doses in 5 planned cohorts were 25 mg, 50 mg, 100 mg, 200 mg and 400 mg. For MAD part, the doses in 3 planned cohorts were determined to be 25mg, 100mg, and 400mg considering the safety and PK profile of RP3128 in SAD.

4 ENDPOINTS

4.1 PRIMARY ENDPOINTS

The primary endpoints for both SAD and MAD parts are as follows:

- Incidence of AEs
- Changes in vital signs (blood pressure, pulse rate, respiratory rate, oral temperature) and weight
- Changes in 12-lead ECG parameters
- Changes in clinical laboratory assessments (hematology, chemistry, urinalysis)

4.2 SECONDARY ENDPOINTS

The secondary endpoints include PK parameters and biomarker assessments

SAD-PK Endpoints:

- Maximum observed plasma concentration (C_{\max})
- Time to maximum observed plasma concentration (T_{\max})
- Area under the plasma concentration-time curve from time zero until the last time point with measurable concentration (AUC_{0-t})
- Area under the plasma concentration-time curve from time zero to infinity (AUC_{0-inf})
- Apparent termination elimination rate constant (K_{el})
- Apparent terminal elimination half-life ($t_{1/2}$)

MAD-PK Endpoints:

- Maximum observed plasma concentration in the dosing interval (C_{\max}) (Day 1, Day 7)
- Lowest observed plasma concentration in the dosing interval (C_{\min}) (Day 7)
- Plasma concentration at the end of the dosing interval (C_{trough}) (Day 3, Day 5, Day 7)
- Average concentration during the dosing interval (C_{av}) (Day 7)
- Time to maximum plasma concentration (T_{\max}) (Day 1, Day 7)
- Area under the plasma concentration-time curve from time zero until the last time point with measurable concentration (AUC_{0-24}) (Day 1, Day 7)
- Degree of fluctuation [$(C_{\max}-C_{\min})/C_{av}$] (Day 7)
- Swing [$(C_{\max}-C_{\min})/C_{\min}$] (Day 7)
- Terminal half-life ($t_{1/2}$) (Day 1, 7)

MAD-Biomarker Endpoints:

- Levels of various biomarkers (Th1, Th2 and Th17 cytokines) following LPS or CD3/CD28 stimulation

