3.3 BRIEF DESCRIPTION

This is a phase I, single-center, double-blind, randomized, placebo-controlled study to evaluate the safety, tolerability, and PK of single or multiple ascending dose (SAD or MAD) of RP3128 in healthy volunteers.

There were 5 cohorts in SAD and 3 cohorts in MAD. In the first part of the study (Part 1, SAD), single dose of RP3128/placebo was administered on Day 1. In the second part (Part 2, MAD), multiple doses of RP3128/placebo were administered once a day from Day 1 to Day 7. In both SAD and MAD, the cohorts were dosed sequentially so that a minimum of 8 days was allowed between dose of previous cohort and the initiation of next cohort. Progression to the next higher dose occurred only after confirming safety, tolerability and PK of existing dose. In case of safety concern, additional subjects may be added to cohort for safety assessment as per the decision of Safety Review Committee (SRC).

In addition, sentinel design was applied. Within each cohort, 2 sentinel subjects was dosed first for safety assessment. Safety and tolerability data up to 24 hours was reviewed along with any observation up to 36 hours by the investigator prior to dosing the remaining subjects at that dose level. The remainder of the cohort was dosed sequentially at least 48 hours after confirming safety and tolerability of sentinel cohort.

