8.2 COLLECTION SCHEDULE

For SAD part, blood samples will be collected for plasma levels of RP3128 on Day 1 (Pre-dose, 0.25, 0.5, 1.0, 2.0, 4.0, 6.0, 8.0, 12.0, 24.0 and 48 hr), Day 5, Day 8 and Day 15. For MAD part, blood samples will be collected for plasma levels of RP3128 on Day 1 (Pre-dose, 0.25, 0.5, 1.0, 2.0, 4.0, 6.0, 8.0, 12.0 and 24.0 hr), Day 3, Day 5, Day 7 (Pre-dose, 0.25, 0.5, 1.0, 2.0, 4.0, 6.0, 8.0, 12.0 and 24.0 hr), Day 9 (48 hr), Day 10 (72 hr), Day 11 (96 hr), Day 12 (120 hr), Day 13 (144 hr) and Day 15 (192 hr).

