8.3 DERIVED DATA AND HANDLING OF MISSING OR BELOW LLOQ DATA

8.3.1 Derivation of PK Parameters

PK parameters for RP3128 will be derived with validated SAS programs for all RP3128 dose levels by non-compartmental analysis of the plasma concentration data using actual sampling times.

The following pharmacokinetic variables will be derived:

SAD:

- Maximum observed plasma concentration (C_{max})
- Time to maximum plasma concentration (T_{max})
- Terminal half-life ($t_{1/2}$)
- Area under the plasma concentration-time curve from time zero until the last measurable time point (AUC_{0-t})
- Area under the plasma concentration-time curve from time zero to infinity time (AUC_{0-inf})
- Elimination rate constant (K_{el})

MAD:

- Maximum observed plasma concentration in the dosing interval (C_{max}) (Day 1, Day 7)

- Lowest observed plasma concentration in the dosing interval (C_{\min}) (Day 7)
- Plasma concentration at the end of the dosing interval (C_{trough}) (Day 3, Day 5, Day 7)
- Average concentration during the dosing interval (C_{av}) (Day 7)
- Time to maximum plasma concentration (T_{max}) (Day 1, Day 7)
- Area under the plasma concentration-time curve from time zero until the last time point with measurable concentration (AUC_{0-24}) (Day 1, Day 7)
- Degree of fluctuation $[(C_{\text{max}}-C_{\min})/C_{\text{av}}]$ (Day 7)
- Swing $[(C_{\text{max}}-C_{\min})/C_{\min}]$ (Day 7)

The PK parameters will be estimated as follows:

- The C_{max} and the corresponding T_{max} , C_{\min} and C_{trough} will be read directly from the concentration-time plot (observed data, not predicted data by the program).
- AUCs will be calculated using the linear trapezoidal rule.
- The terminal elimination rate constant (K_{el}) will be determined by log linear regression obtained on at least the 3 last quantifiable concentrations and will not include C_{max} . The adjusted square of the correlation coefficient (R-square adjusted) for the goodness of fit of the regression line through the data points must be at least 0.80 for the K_{el} value to be considered reliable. If fewer than 3 quantifiable concentrations are available after C_{max} or if R-square is less than 0.80, the K_{el} will be left uncalculated.
- $t_{1/2}$ is calculated by the program as $\ln 2 / K_{\text{el}}$. If K_{el} is not calculable, then $t_{1/2}$ will also remain missing.
- The AUC from 0 to infinity is calculated by the program as:

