¹Mean calculated based on number of subjects (N).

Programming Note: X will be assigned as 1, 2, 3.... as per each RP3128 dose level. Time point may vary depending the actual data.

<Dose Level> = RP3128 25mg, 100mg, 400mg in MAD

Table 14.2.1.2.X.S RP3128 – Summary of PK Parameters (SAD)

**PK Population
<Dose Level>**

Cohort/Subject	AUC _{0-t} (h*ng/mL)	AUC _{0-inf} (h*ng/mL)	C _{max} (ng/mL)	T _{max} (h)	K _{el} (1/h)	T _{1/2} (h)
xxxx	xxx	Xxx	xxx	xxx	xxx	xxx
xxxx	xxx	Xxx	xxx	xxx	xxx	xxx
....	xxx	Xxx	xxx	xxx	xxx	xxx
Statistics						
N	xx	xx	xx	xx	xx	xx
Mean	xxx.x	xxx.x	xxx.x	xxx.x	xxx.x	xxx.x
SD	xxx.xx	xxx.xx	xxx.xx	xxx.xx	xxx.xx	xxx.xx
CV (%)	xx.x	xx.x	xx.x	xx.x	xx.x	xx.x
Minimum	xxx	xxx	xxx	xxx	xxx	xxx
Median	xxx.x	xxx.x	xxx.x	xxx.x	xxx.x	xxx.x
Maximum	xxx	xxx	xxx	xxx	xxx	xxx
Geo Mean ¹	xxx.x	xxx.x	xxx.x	NA	NA	NA
Geometric CV%	xx.x	xx.x	xx.x	NA	NA	NA

N=Number of subjects with derivable PK parameter.

<Dose Level> = RP3128 25 mg, 50 mg, 100 mg, 200 mg, 400 mg

Programming Notes: Geometric mean shall be calculated for all PK parameters except T_{max}, t_{1/2} and K_{el}. T_{max} will only have n, median, min, max provided.

X will be assigned as 1, 2, 3.... as per each RP3128 dose level.

**Table 14.2.1.2.1.X.M RP3128 – Summary of PK parameters (MAD) – Day 1
PK Population
<Dose Level>**

Cohort/Subject	C _{max} (ng/mL)	AUC ₀₋₂₄ (ng·h/mL)	T _{max} (h)	T _{1/2} (h)
xxxx	xxx	xxx	xxx	xxx
xxxx	xxx	xxx	xxx	xxx
Statistics				
N	xx	xx	xx	xx
Mean	xxx.x	xxx.x	xxx.x	xxx.x
SD	xxx.xx	xxx.xx	xxx.xx	xxx.xx
CV (%)	xx.x	xx.x	xx.x	xx.x
Minimum	xxx	x.x	x.x	x.x
Median	xxx.x	xx.x	xx.x	xx.x
Maximum	xxx	x.x	x.x	x.x
Geo Mean ¹	xxx.x	xxx.x	NA	NA
Geometric CV%	xx.x	xx.x	NA	NA

N=Number of subjects with derivable PK parameter.

¹: Geo Mean: Geometric means are based on the arithmetic means of ln-transformed values

Programming Note: <Dose Level> = RP3128 25mg, 100mg, and 400mg.

X will be assigned as 1, 2, and 3 as per each RP3128 dose level.

**Table 14.2.1.2.2.X.M RP3128 – Summary of C_{trough} (MAD)
PK Population
<Dose Level>**

Cohort/Subject	C _{trough} (ng/mL)		
	Day 3	Day 5	Day 7
xxxx	xxx	xxx	xxx
xxxx	xxx	xxx	xxx
Statistics			
N	xx	xx	xx
Mean	xxx.x	xxx.x	xxx.x
SD	xxx.xx	xxx.xx	xxx.xx
CV (%)	xx.x	xx.x	xx.x
Minimum	xxx	xxx	x.x
Median	xxx.x	xxx.x	xx.x
Maximum	xxx	xxx	x.x
Geo Mean ¹	xxx.x	xxx.x	xxx.x
Geometric CV%	xx.x	xx.x	xx.x

N=Number of subjects with derivable PK parameter.

¹: Geo Mean: Geometric means are based on the arithmetic means of ln-transformed values

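### The MAD Day 1 terminal half-life rests on a 24 h profile with no minimum fitting span, so it is likely to be too short or uncalculable if the half-life is about 24 h or longer

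*SAP*

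**What the plan says.** - **Endpoint.** The MAD PK endpoints in section 4.2 include "Terminal half-life ($t_{1/2}$) (Day 1, 7". The shell titled "RP3128 – Summary of PK parameters (MAD) – Day 1" (Table 14.2.1.2.1.X.M) has a half-life column, as does the Day 7 shell (Table 14.2.1.2.3.X.M).
- **Dosing.** Section 3.3 states that "multiple doses of RP3128/placebo were administered once a day from Day 1 to Day 7", so the second dose follows 24 h after the first.
- **Sampling.** Section 8.2 gives the MAD times as "Day 1 (Pre-dose, 0.25, 0.5, 1.0, 2.0, 4.0, 6.0, 8.0, 12.0 and 24.0 hr), Day 3, Day 5, Day 7". After the Day 7 dose, sampling continues through "Day 13 (144 hr) and Day 15 (192 hr". In SAD the late samples are "24.0 and 48 hr), Day 5, Day 8 and Day 15"; Day 15 is 14 × 24 = 336 h, as the SAD concentration shell shows.
- **Kel rule.** Section 8.3.1 bases Kel on "log linear regression obtained on at least the 3 last quantifiable concentrations", excluding Cmax. The adjusted R-square "must be at least 0.80 for the K_{el} value to be considered reliable"; otherwise Kel and half-life stay missing. No minimum span is set, and Day 1 has no rule of its own. The 20% limit on extrapolation applies to AUC to infinity, which is not a MAD endpoint.
- **Derivation list.** The MAD list in section 8.3.1 contains neither Kel nor half-life, although section 4.2 and both shells require half-life.

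**The concern.** The same label, terminal, is given to a slope from a window that dosing closes at 24 h and to a slope that can use 192 h. If RP3128 declines slowly, the last three Day 1 samples (8, 12 and 24 h) cover only a fraction of one half-life. The slope may then reflect distribution rather than elimination, or be too shallow relative to assay noise to pass the R-square rule. The Day 1 column would then hold short values, values from a selected few subjects, or blanks. Anyone reading it against Day 7 could take the difference for a half-life that lengthens on repeat dosing, when only the sampling window has changed.

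**Working it through.** The SAP gives no half-life, so there is no figure of its own to reproduce. The check applies the section 8.3.1 rule to assumed profiles.

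**Inputs from the SAP.** Day 1 times 0.25 to 24 h; Day 7 times to 192 h after seven daily doses; a log-linear fit to the last three points, with at least three points after Cmax; adjusted R-square at least 0.80; half-life = ln 2 / Kel; 6 active subjects per MAD cohort (section 3.6).

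**Assumptions, not in the SAP.** True terminal half-life 8 to 96 h; first-order absorption with ka 1.0 or 0.3 per h; one phase, or two phases with an initial half-life of 3 or 6 h carrying 50% or 80% of the intercept; 15% CV sampling error where noise is added.

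**Step 1: span.** The last three Day 1 points span 24 − 8 = 16 h. That is 16/24 = 0.67 half-lives at 24 h, 16/48 = 0.33 at 48 h and 16/96 = 0.17 at 96 h. The 192 h after the Day 7 dose give 8, 4 and 2 half-lives.

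**Step 2: one case in full.** Let C(t) = Σ fᵢ·ka/(ka − λᵢ)·(exp(−λᵢt) − exp(−ka·t)), with ka = 1.0, initial half-life 3 h (50%) and true terminal half-life 24 h. Then λ₁ = 0.2310 and λ₂ = 0.02888.
- C(8) = 0.5107, C(12) = 0.4047, C(24) = 0.2600; logs −0.6720, −0.9046, −1.3472.
- Mean time 14.667; Sxx = 138.667; Sxy = −5.681; slope = −0.04097.
- Half-life = 0.6931/0.04097 = 16.9 h against a true 24 h. Adjusted R-square is 0.979, so the fit is accepted.

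**Step 3: two-phase decline, no noise, ka 1.0 (range over the four initial phases).**

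| True half-life | Day 1 value | Share of true |
|---|---|---|
| 24 h | 9.5 to 16.9 h | 40% to 70% |
| 48 h | 11.4 to 27.2 h | 24% to 57% |
| 96 h | 12.8 to 39.0 h | 13% to 41% |

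Adjusted R-square is 0.86 to 0.997, so the 0.80 filter removes none of these.

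**Step 4: one-phase decline, 15% CV noise, ka 1.0.** Repeat simulations differ slightly, so ranges are given.

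| True half-life | Day 1 uncalculable | Median when calculable |
|---|---|---|
| 8 h | 4% | 8.0 h |
| 12 h | 19% to 20% | 11.8 h |
| 24 h | 56% to 60% | about 22 h |
| 48 h | 80% | 34 to 35 h |
| 96 h | 89% | 43 to 44 h |

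With a slow decline, the R-square filter keeps mainly profiles whose noise steepens the slope. Of 6 active subjects, the expected number with a value is 6 × 0.40 to 0.44 = 2.4 to 2.6 at 24 h, 6 × 0.20 = 1.2 at 48 h and 6 × 0.11 = 0.7 at 96 h.

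**Step 5: cases without that bias.** One phase, no noise, ka 1.0 returns 24.0 h for 24 h and 48.1 h for 48 h. One phase with ka 0.3 returns 14.0 h for a true 12 h, which is too long, and nothing at 24 h or more, because fewer than three samples follow Cmax.

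**Step 6: Day 7, same rule.** Without noise, every assumed half-life is recovered to within 0.1 h. With 15% noise and a true 24 h, the median is 24.0 h and none is uncalculable. At a true 96 h, 43% are uncalculable and the median is about 86 to 87 h.

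Letting the fit choose three or more points by best adjusted R-square gave similar results.

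**The case against.** The strongest reply is that the document gives no half-life. Late sampling shows where the sponsor chose to look, not how slowly the drug declines, and the SAD late samples fall on the ambulatory visit days. A reader might infer that the Day 1 profile cannot reach the terminal phase and must give too short a value. The SAP does not support that: Step 5 shows cases with no bias or with the opposite sign. This stands, and it makes the point conditional.

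A reader might also infer that the bias would go unseen. That does not hold. Section 8.5 promises the fit statistics and time window by subject and cohort without limiting them to SAD. The Day 1 shell shows individual values and defines N as subjects with a derivable parameter, Listing 16.2.5.4.S/M gives reasons for missing parameters, and individual semi-logarithmic plots are planned for MAD. What remains is that the only shell carrying the fit window, Listing 16.2.5.3.S, is for SAD only.

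Nor does the SAP support a claim that accumulation would be understated. It plans no prediction from half-life and no test of Day 1 against Day 7; the two sit in separate descriptive tables. Accumulation can be read from Day 1 and Day 7 AUC and from the trough values. SAD also gives single-dose half-lives at the same 25, 100 and 400 mg levels, so an apparent lengthening could be checked. These points reduce the consequence. They also show how little would be lost by dropping the Day 1 value.

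**Conclusion.** The point holds in conditional form. If the terminal half-life is about 24 h or longer, which sampling to 192 h and 336 h suggests but does not prove, the Day 1 MAD value is likely to be too short or uncalculable and is not comparable with Day 7. Under the assumed two-phase declines with fast absorption, it is 13% to 70% of the true value for half-lives of 24 to 96 h. Under one-phase decline with 15% noise, 56% to 89% of subjects would have no value. For a one-phase half-life of about 12 h or less with fast absorption, the bias is negligible. That exception depends on there being one phase: with a 3 h initial phase carrying 80% of the intercept, a true 12 h is reported as 6.9 h. All these sizes rest on assumed disposition, absorption and noise.

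Independently of any half-life, the MAD derivation list in section 8.3.1 disagrees with section 4.2 and the shells, and the Kel diagnostics shell falls short of section 8.5.

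**What to change.** 1. In section 4.2, drop Day 1 from the MAD terminal half-life endpoint and remove that column from Table 14.2.1.2.1.X.M. Alternatively, keep it relabelled as an apparent half-life over 0-24 h, with a footnote that it is not to be compared with Day 7.
2. Take the MAD terminal half-life from Day 7, using samples to 192 h.
3. Add Kel and half-life (Day 7) to the MAD list in section 8.3.1.
4. Extend Listing 16.2.5.3 to MAD, as section 8.5 already implies.

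A minimum regression span relative to the estimated half-life would be a useful addition to the Kel rule. As an illustration, a requirement of two half-lives (an assumed convention, not in the SAP) would limit a 16 to 20 h Day 1 window to half-lives of about 8 to 10 h.

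The cost is SAP and shell wording, one extra listing and at most one descriptive column. No data collection changes. If the half-life is short, Day 7 and SAD already supply it. If it is very long, Day 7 is also imperfect (Step 6), but it remains better than Day 1.

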5 ANALYSIS POPULATION

5.1 RANDOMIZED POPULATION

The randomized population consists of all eligible subjects who are randomized to receive a treatment regardless whether they are actually treated. These subjects are grouped by their randomized treatment group. The randomized population will be used to summarize subject disposition from randomization through termination.

5.2 SAFETY POPULATION

The Safety population will include randomized subjects who receive at least one dose of study drug (RP3128 or placebo) during treatment phase. Subjects will be analyzed as treated, if any subjects received the study drug different from the drug they were randomized to receive. There will be separate safety populations each for SAD and MAD parts. The Safety population will be used for all analyses of safety endpoints, biomarker endpoints, as well as demographics and baseline characteristics.

5.3 PHARMACOKINETIC (PK) POPULATION

The PK population will include all safety subjects with sufficient concentration-time data to determine PK parameters and no major protocol deviations. The PK population will be used for all analyses of PK endpoints.

5.4 PROTOCOL DEVIATIONS

All protocol deviations related to study inclusion or exclusion criteria, conduct of the trial, subject management or subject assessment will be listed. The list of protocol deviations will be reviewed by the Sponsor, the PI, the study statistician and the study scientist before unblinding the study.

6 GENERAL ASPECTS FOR STATISTICAL ANALYSIS

6.1 SUMMARY STATISTICS

The standard summary statistics that will be calculated for quantitative and qualitative variables are:

- Quantitative:
 - Standard Statistics for both Safety/PK: Number of subjects, mean, median, standard deviation (SD), minimum and maximum of the raw data
 - Additional Statistics for PK: coefficient of variance (PK concentration and PK parameters), geometric mean, and geometric CV (%) (PK parameters AUC and C_{max} in SAD part and AUC₀₋₂₄, C_{max}, C_{min}, C_{trough} in MAD part)
- Qualitative: number of subjects (n), number of missing observations (nmiss), absolute and relative frequencies (%) per category.

Demographics and disposition will be summarized by treatment group and overall.

Data collected pre- and post-dose during the treatment period (e.g., vital signs, ECG, and clinical laboratory) will be summarized by treatment group (dose level), visit and/or time point. For quantitative variables (ECG measurements, vital signs, hematology, etc.), change from baseline will be calculated and summarized by treatment, visit and/or time point together with baseline and post-dose value. For qualitative variables (e.g., ECG interpretation, urinalysis), standard summary of frequencies will be calculated by treatment, visit and/or time points. For safety lab data only, shift table will be produced to present the change of reference range indicator from baseline to post-dose. PK parameters will be summarized by treatment group, and visit (if applicable). All subjects assigned and treated with Placebo in different cohorts will be pooled together and summarized as a single group.

6.1.1 Summary Statistics Reporting Precision

Summary statistics will be presented to the following degree of precision:

Table 1. Reporting Precision

Statistics	Degree of Precision
Mean (of all kinds), Median	One more decimal place than the raw data
Standard deviation, Standard error	Two more decimal places than the raw data

Minimum, Maximum	The same number of decimal places as the raw data
Percent, Coefficient of Variance	Two decimal places for PK parameters, and one decimal place for all other parameters
PK Concentration, AUC, Cmax	The same number of decimal places as LLOQ

All fractional numeric values will be presented with a zero to the left of the decimal point (for example, 0.12, - 0.30, not .12, - .30).

6.2 KEY DEFINITIONS

The day of administration of the first dose of study drug during the treatment period is defined as Study Day 1. Study Day -1 is the day before dosing, all assessments prior to Study Day 1, including the Screening and Check-in Visits, will have negative study days.

The baseline observation will be the last non-missing value prior to the first dose of study drug.

Nominal Time is the scheduled measurement time relative to time 0. Time 0 is precisely defined for each analysis below.

For AEs, onset time from dosing will be calculated as the difference between the event and dosing start date/time. Onset time from dosing will be expressed in days, hours and minutes. If time is missing, onset time from dosing will be calculated as the difference between the start date and dosing date plus 1 and expressed in days when the event date is on or after the dosing date; otherwise, onset time from dosing will be calculated only as difference between the start date and dosing date and expressed in negative numbers.

Duration will be calculated for AEs that resolve as the difference between the AE resolution date/time and onset date/time and will be expressed in days, hours and minutes. If time is missing, duration will be calculated as the difference between the resolution date and onset date plus 1 and expressed in days. AE onset time from dosing and duration of AE will only be derived when both start and end dates are complete.

